The control group will also receive the pre-tests on the first day and post-tests 14 days later. They will not receive any treatment in that period, and they are not instructed to do or not to do anything in particular while at home. This means that the control group participants will proceed with their daily life as normally. The usability questionnaires will only be administered to the experimental group, not to the control group.

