## **Plan for Statistical Analysis**

The analysis of the Barcelona test and the Communicative Activity Log (CAL) will consist primarily of within-group analyses with the Wilcoxon rank sum test, because of the low number of subjects. Additionally, linear mixed effects models will be used for the between-group analyses, with the Barcelona Test and the CAL score for each domain (patient, family, and therapist), respectively, as the dependent variable. The main independent variable will be the pre-/post-test (time) through binary coding, as well as the control versus the experimental group, including the interaction between the time variable and the group. The participant ID will be included as random intercept in the model, to account for differences between participants. The validity of the regression analysis will be evaluated by testing the residuals of the model for normality using the Shapiro-Wilk test for normality. Given the low number of subjects, the descriptive statistics will be reported with medians and quartiles, as with non-parametric tests.

A descriptive analysis will be made of the SUS and MAUQ usability questionnaires to determine the potential of a mobile application by drawing general conclusions from the use of this specific application. These will be analysed with computation of overall scores and examination of scores of different qualities of the application and use.

Further analysis will consist of descriptive statistics of the use of the application, e.g., amount of use, reaction times, and recording length, for participants in the experimental groups. The variables will be checked for normality with the Shapiro-Wilk test and depending on the results either means and standard deviation or medians and quartiles will be reported. The use measures will be analysed with t-tests or Wilcoxon rank sum tests to evaluate whether they changed over time with the use of the application.

An additional analysis will be made of the score differences for the Barcelona test of the experimental group, where the amount of use will be included in a linear regression model. With the difference in test score as the dependent variable, the independent variables included will be the total amount of use of the application. This analysis will evaluate whether the amount of use influenced the outcome of the treatment.

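### Does the Shapiro-Wilk check on the mixed-model residuals need replacing because it can miss skewed change scores?

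*Combined protocol and SAP*

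**What the plan says.** The between-group analysis of the Barcelona test and of each CAL domain (patient, family, therapist) is a linear mixed model. On time, the Plan for Statistical Analysis says "The main independent variable will be the pre-/post-test (time) through binary coding". Group is also a factor, "including the interaction between the time variable and the group". On the random part it says "The participant ID will be included as random intercept in the model".

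The only diagnostic named for this model is: "The validity of the regression analysis will be evaluated by testing the residuals of the model for normality using the Shapiro-Wilk test". The plan does not say whether the residuals are conditional or marginal, and gives no action on a pass or a fail. For the app-use variables, the third paragraph does state a consequence of the same test: "depending on the results either means and standard deviation or medians and quartiles will be reported".

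The mixed model is additional. Within-group rank tests are primary, "because of the low number of subjects". The mixed model is nevertheless the only comparison of app users with controls, of whom the Study Protocol says "They will not receive any treatment in that period".

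**The concern.** With two visits, the time-by-group interaction is the difference between arms in mean change. The distribution that matters for that test is therefore the distribution of each person's change. Residuals from a random-intercept model hide its shape: the two conditional residuals of one person are close to plus and minus half the centred change, so a right-skewed change gives a nearly symmetric pooled set. The pairs are also not the independent sample that Shapiro-Wilk assumes.

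A pass could then be taken as evidence that the model is valid when it says little about skew. A fail would leave the response to be chosen after the data are seen. Since this is the only controlled comparison, the worry is false reassurance and, if changes are skewed, some loss of efficiency.

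**Working it through.** **Inputs.** From the documents: two visits, random intercept, time-by-group interaction, Shapiro-Wilk on model residuals. Not in the documents, so assumed: 10, 15 or 20 per arm; alpha 0.05; intraclass correlation (ICC) 0.6 to 0.9; change normal, gamma (skewness 1), exponential (skewness 2) or lognormal. The plan has no figure of its own to reproduce.

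**Step 1: why skew cancels.** For person *i*, let *m* be the mean and *d* the difference (post minus pre) of the two deviations from the fitted group-by-time means. The predicted intercept is λ*m*, with λ = 2·ICC/(1 + ICC). The conditional residuals are

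- pre: (1 − λ)*m* − *d*/2
- post: (1 − λ)*m* + *d*/2

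Their correlation is −λ/(2 − λ) = −ICC. At ICC 0.8, λ = 1.6/1.8 = 0.889, and −0.889/1.111 = −0.80. In the pooled third moment the *d*³ terms have opposite signs and drop out, which leaves (1 − λ)³E[*m*³] + (3/4)(1 − λ)E[*md*²]. Both terms are small when ICC is high.

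**Step 2: what the check detects.** Simulation at ICC 0.8, with 10/15/20 per arm and the same change distribution in both arms:

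| Change distribution | Pooled conditional residuals | Group-centred changes |
|---|---|---|
| gamma, skewness 1 | 7/10/13% | 25/40/53% |
| exponential, skewness 2 | 19/34/46% | 70/91/98% |
| lognormal | 42/67/81% | 85/97/100% |

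A fresh run of 3,000 trials per cell agreed within simulation error (gamma 6/11/13% against 24/40/54%). Marginal residuals do not help: they reject exactly normal data in 6 to 17% of trials, and gamma skew moves that rate by at most about 1.5 points. For symmetric heavy tails the gap is smaller: with *t* on 3 degrees of freedom, 19/37/47% against 29/44/53%.

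**Step 3: what a missed departure does to the result.** In this balanced design the interaction test is the two-sample *t*-test on change. Its type I error at nominal 5% was:

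- 3.2 to 6.2% in all settings tried but one (20,000 runs each).
- The exception was lognormal change in the app arm only, with 10 controls and 20 app users: 8.3%. A fresh run of 20,000 gave 8.0%, and a smaller run of 1,000 gave about 10%.
- With skew and a doubled standard deviation in one arm, 10 to 40 participants in total: 5.5 to 7.9%.

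**Step 4: what the alternatives would change.** Replacing the check changes no estimate, interval or p-value, because the plan does not let the check choose the analysis. Adding a rank-sum test of change would give this power at 15 per arm for a mean shift of 0.8 SD, or for a quarter responding by 3 SD (last row):

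| Setting | *t*-test | Rank-sum |
|---|---|---|
| normal | 56% | 52% |
| exponential, both arms | 60% | 76% |
| lognormal, both arms | 71.8% | 94.5% |
| exponential, app arm only | 57% | 49% |
| lognormal, app arm only | 62% | 57% |
| 25% responders at +3 SD | 29% | 20% |

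With equal means and skew in the app arm only, the rank test rejects in up to 8.0% of trials (equal arms) or 9.6% (10 against 20). In the lognormal 10-against-20 case, the run of 1,000 gave about 12% for the rank test, against about 10% for the *t*-test.

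**The case for a change.** The strongest case for a change is that this is the only comparison with untreated controls, that its one named check is poorly aimed, and that a remedy costs a sentence or two. The plan already uses change scores for the app group in the amount-of-use regression ("With the difference in test score as the dependent variable"), so checking them by group would be easy. If skew were shared by both arms, a rank test would also gain real power: 76 − 60 = 16 points for exponential change and 94.5 − 71.8 = 22.7 points for lognormal.

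Much of this stands. The mechanism follows from the planned model, and a pass is weak evidence of normality. Three points keep it from requiring a change.

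- The efficiency loss belongs to the choice of a mean-based model, not to the check. A sharper check that leaves the interaction as the reported result recovers none of it.
- Since untreated controls cannot be app responders, skew caused by treatment would arise in the app arm only. There the rank test does worse: 57 − 49 = 8, 62 − 57 = 5 and 29 − 20 = 9 points lost in the three settings above. It also tests a different hypothesis from the difference in means.
- In that same setting the group-centred check is itself weak: at 10/15/20 per arm it finds gamma skew in 11/15/19% and exponential skew in 26/37/47%.

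The missing residual type and the missing consequence are gaps in detail. The plan presents the check as bearing on the validity of the regression, so the sensible reading is that a failure is reported and qualifies how the interaction is described. An analyst would normally look at the changes by group as well.

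**Conclusion.** No change is needed. Shapiro-Wilk on these residuals is an insensitive check of skew in the change scores, with roughly a quarter to a half of the detection rate of the better-aimed test at 15 per arm (10/40 = 0.25 for gamma, 34/91 = 0.37 for exponential) and a smaller shortfall for lognormal (67/97 = 0.69) and for heavy tails. But it decides nothing, and the test it accompanies is close to nominal in nearly all settings tried, with a worst case of about 8 to 10% in one extreme unequal-arm scenario. Reassurance about the p-value is therefore largely correct even when the check misses the skew. The rank-sum test is a fair optional sensitivity analysis, but a trade-off and not a correction.

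The conclusion rests on assumed sample sizes, ICC, alpha and change distributions, and on reading the plan as testing all residuals of each model together. It would need another look if the check were used to switch between analyses, or if the arms proved very unequal in size with strong skew in one of them.

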## **Study Protocol**

Therapy will be administered to participants through a mobile application which all participants in the experimental group will use at home for two weeks. Before starting the use, pre-tests are conducted to determine the baseline scores of language function and communication using the Barcelona test and the Communicative Activity Log. In the introductory session, after the tests, the application is installed on the participant's own phone and the participant is given instructions and trained in how to use the application, before starting their individual use of it at home. The therapist will prescribe use of the application 2 times per day for 20 minutes. Support is made available during the two weeks, if the participant is having issues with the use of the application. Furthermore, all patients are informed that they are allowed to receive help from family members or others in using the application at home.

The participant is instructed to use the application two times every day for about twenty minutes, but although this was the recommended use, the participant is free to use the application when and for as long as they want. While using the app, the participant will, through the app, be informed when they have been practicing for twenty minutes, in order to limit their use to shorter but more frequent sessions. The practice consists of several different tasks that are connected to different contexts from everyday life. The tasks consist of matching visual objects, sounds, and short videos, as well as some written input of words. The tasks also ask participants to record their voice saying the name of the object and to listen to and evaluate their recording.

After two weeks, the participants will return and be given post-tests on the same measures as before the start of the treatment, i.e., clinical scales for assessing language function and communication. Additionally, they will complete two usability questionnaires (the System Usability Scale and the mHealth App Usability Questionnaire), and a few questions regarding risk assessment.

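### The primary within-group analysis of Barcelona and CAL names no estimate or interval for within-person change, and does not say whether its medians describe visit scores or changes

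*Combined protocol and SAP*

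**What the plan says.** In the Combined protocol and SAP, Plan for Statistical Analysis, paragraph 1, the analysis of the Barcelona test and the CAL "will consist primarily of within-group analyses with the Wilcoxon rank sum test, because of the low number of subjects". The same paragraph closes with the rule for summaries: "Given the low number of subjects, the descriptive statistics will be reported with medians and quartiles, as with non-parametric tests".

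The design is paired in both groups. Under Study Protocol, the experimental group returns after two weeks to "be given post-tests on the same measures as before the start of the treatment". For controls: "The control group will also receive the pre-tests on the first day and post-tests 14 days later".

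Paragraph 1 also plans a model: "Additionally, linear mixed effects models will be used for the between-group analyses". It covers Barcelona and each CAL domain, with time and group as terms, "including the interaction between the time variable and the group". On pairing it says: "The participant ID will be included as random intercept in the model, to account for differences between participants".

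Individual change scores appear explicitly only in the last paragraph of the plan. They are used there for Barcelona, in the experimental group, as the outcome of a regression on amount of app use.

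**The concern.** Each participant is measured twice, so the quantity of interest is the change within a person. For the primary analysis the plan commits to a rank test and to medians and quartiles of something it does not specify. If these are medians of the pre scores and of the post scores, the obvious measure of benefit on the page is the gap between them. That gap is not the median change. It ignores who scored what at which visit, varies more from sample to sample than a paired estimate, and comes with no interval.

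This matters most in a small study, which the plan says this is. A p-value without an interval cannot separate no effect from a useful effect estimated imprecisely. A table of visit medians could also show an apparent loss where most participants improved.

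**Working it through.** The documents state no sample size, SD, correlation, alpha or expected effect, so there is no planned figure to reproduce. All numerical inputs below are assumptions.

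**1. Can the two summaries conflict?** A constructed example with seven participants:

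| | 1 | 2 | 3 | 4 | 5 | 6 | 7 |
|---|---|---|---|---|---|---|---|
| Pre | 20 | 30 | 50 | 60 | 62 | 80 | 90 |
| Post | 24 | 33 | 55 | 57 | 66 | 85 | 94 |
| Change | +4 | +3 | +5 | -3 | +4 | +5 | +4 |

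- Gap between medians: 57 - 60 = -3.
- Median change: +4. Mean change: 22/7 = +3.1. Hodges-Lehmann estimate (median of all pairwise averages of the changes): +4.

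Six of seven participants improve, yet the visit medians fall.

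**2. How often would this happen?** Simulated normal pre and post scores with SD 1, 20,000 trials per row, comparing the gap between medians with the median paired change. The variance ratio is (SD of gap / SD of median change)², taken at a gain of 0.2 SD.

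| n | Correlation | Opposite sign, gain 0.2 SD | Opposite sign, gain 0.3 SD | Variance ratio |
|---|---|---|---|---|
| 10 | 0.8 | 22.5% | 15.9% | (0.305/0.237)² = 1.7 |
| 10 | 0.9 | 19.1% | 10.7% | (0.236/0.166)² = 2.0 |
| 15 | 0.8 | 23.0% | 15.6% | (0.282/0.202)² = 1.9 |
| 15 | 0.9 | 19.3% | 10.0% | (0.231/0.142)² = 2.6 |
| 20 | 0.8 | 19.9% | 10.5% | (0.234/0.171)² = 1.9 |
| 20 | 0.9 | 15.0% | 5.7% | (0.188/0.122)² = 2.4 |

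Against the Hodges-Lehmann estimate, over the same settings, signs disagree in about 5% to 21% of trials and the variance ratio is about 2.2 to 4.1.

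**3. What does the mixed model supply?** The model is score = b0 + b1·time + b2·group + b3·(time × group) + participant intercept + error. With complete data at both visits, b1 is the mean change in the reference group and b3 is the between-group difference in mean change. A simulated fit with 8 per group confirms this:

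- b1 = 0.174, and the reference group's mean paired change = 0.174.
- b3 = 8.034, and the difference in mean paired change = 8.034.
- Wald 95% intervals are available from the fit: -2.04 to 2.39 for b1, and 4.91 to 11.16 for b3.

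So a paired estimate exists in the plan. A commitment to report it with an interval does not.

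**4. Which test would accompany a paired estimate?** The plan names the rank sum test. Taken literally, that test treats pre and post scores as independent samples. In the example in step 1:

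- Rank sum: p = 0.80.
- Signed-rank: the negative rank sum is 1.5 (tied ranks averaged). Three of the 2⁷ = 128 sign patterns give a value that small, so p = 2 × 3/128 = 0.047.

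A Hodges-Lehmann interval for paired change corresponds to the signed-rank test and not to the rank sum test.

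**The case against.** The strongest reply is that the mixed model already covers every outcome, respects the pairing, and yields both mean change and the between-group difference. This stands. A reader might infer from the primary analysis that the plan has no estimate of change within or between groups. Paragraph 1 does not support that. What remains is that the model has an additional, between-group role and that no interval from it is promised.

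Second, the sentence on medians does not say they are visit medians. If medians of change are meant, the sign conflict disappears. This also stands, and it is why the point is about an unspecified summary. Even on that reading, no interval is planned.

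Third, the size depends on the inputs. At a gain of 0.5 SD, with the same sample sizes and correlations, sign disagreement drops to about 0.4% to 5%. At correlation 0.5 the variance ratio against Hodges-Lehmann is about 1.6 to 1.9. Part of that ratio is the efficiency of Hodges-Lehmann under normality and not lost pairing, as the smaller ratios in the table show. Nor is disagreement always the medians' fault. With 10 participants, correlation 0.8 and a gain of 0.2 SD, the paired estimate itself shows no gain or a loss in 17% of trials, against 26% for the medians. All of this limits the size of the problem but does not remove it.

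A reader might also infer that model coefficients differing from the reported medians is a fault. It is not: means and medians differ in general, and describing with one while modelling the other is ordinary practice.

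**Conclusion.** The point holds as a modest reporting gap. The primary within-group analysis has no stated effect estimate or interval, and the descriptive summary is ambiguous between visit scores and changes. If visit medians are reported, the gap between them is less precise than a paired estimate and may contradict its direction. How often depends on inputs that the documents do not give: roughly one trial in twenty to one in five under the small-gain, high-correlation settings, and far less often with larger gains. The documents do not show that the gap between medians will be presented as the effect. The between-group comparison is not left without an estimate; it lacks only a promise to report that estimate with an interval. The design and the data to be collected are unaffected.

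**What to change.** In Plan for Statistical Analysis, paragraph 1:

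- Keep medians and quartiles to describe scores at each visit, and say that this is what they describe.
- For each group and each outcome (Barcelona and each CAL domain), add the median and quartiles of post minus pre, and the paired Hodges-Lehmann estimate with its 95% confidence interval.
- Name the Wilcoxon signed-rank test for these within-group comparisons, so that test and interval match and the pairing is used.
- Report the mixed-model time-by-group estimate with its 95% confidence interval.
- State that conclusions about size of effect rest on these estimates and not on the gap between visit medians.

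The cost is a few sentences in the plan and a few table columns. No new data are needed.

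### The plan names the Wilcoxon rank sum test, which assumes independent samples, for two comparisons made within the same participants: the primary pre/post analyses and the change in app-use measures

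*Combined protocol and SAP*

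**What the plan says.** The point concerns two sentences under Plan for Statistical Analysis.

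- **First paragraph.** The Barcelona test and the CAL are analysed primarily by "within-group analyses with the Wilcoxon rank sum test, because of the low number of subjects". Under Study Protocol, each participant is tested before and after the two weeks, so each has one pre and one post score.
- **Third paragraph.** "The use measures will be analysed with t-tests or Wilcoxon rank sum tests to evaluate whether they changed over time". The measures are "amount of use, reaction times, and recording length, for participants in the experimental groups". They come from "a mobile application which all participants in the experimental group will use at home for two weeks".

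The same section does allow for repeated values from one person in the between-group mixed models for Barcelona and CAL: "The participant ID will be included as random intercept in the model, to account for differences between participants". No such provision is made for the use measures. Pairing and the signed-rank test are mentioned nowhere. For the use measures the plan names neither the periods to be compared nor the unit (participant, session or single task record).

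**The concern.** A rank sum test takes its null distribution from two separate sets of people. Here there is one set, measured twice or more. Stable differences between people are then counted as noise, although they cancel when each person is compared with themselves. An analyst who follows the text literally runs the wrong test.

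The first paragraph carries more weight, because it governs the analyses that the plan puts first. The plan itself stresses that subjects are few, which is where lost power costs most. The use-log analysis is secondary, but there the unnamed unit adds a second uncertainty, since reaction times and voice recordings arise task by task ("The tasks also ask participants to record their voice saying the name of the object").

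**Working it through.** The plan gives no figure to reproduce. It states no sample size, effect size or within-person correlation, so every number below is illustrative.

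**1. Why pairing matters.** Let each period's value have standard deviation σ across n participants, with within-person correlation ρ.

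- Variance of the mean change, as an unpaired test assumes it: 2σ²/n.
- True variance of the mean change: 2σ²(1 − ρ)/n.
- Ratio: 1/(1 − ρ), which is 1.0, 1.4, 2.0, 3.3 and 10 at ρ = 0, 0.3, 0.5, 0.7 and 0.9.

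For ρ > 0 the unpaired test overstates its own error. It then rejects too rarely, both when there is no change and when there is one.

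**2. Size of the loss with one value per participant per period.** Simulation with 40,000 runs per cell: bivariate normal values, SD 1, two-sided 5%, exact tests, true change 0.5 SD. Each cell gives power for rank sum / signed-rank.

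| Correlation | n = 10 | n = 15 | n = 20 |
|---|---|---|---|
| 0 | 16% / 16% | 24% / 24% | 32% / 31% |
| 0.3 | 13% / 21% | 20% / 32% | 30% / 41% |
| 0.5 | 11% / 28% | 18% / 41% | 27% / 54% |
| 0.7 | 8% / 43% | 14% / 62% | 24% / 76% |

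- With no true change, the rank sum test rejects in about 4.5% to 5% of runs at correlation 0, 0.8% at 0.5, and 0.1% to 0.2% at 0.7.
- An unpaired against a paired t-test behaves alike. At correlation 0.7 power is 9 / 15 / 25% against 45 / 64 / 78% for n = 10 / 15 / 20.
- For a change of 1 SD at correlation 0.7 the gap narrows as n grows: 55 / 83 / 96% against 94 / 99 / 100%.
- A separate simulation with a change of 0.8 SD and n = 10 gave 32% against 60% at correlation 0.5.

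**3. Use measures, if single records were pooled as independent.** The plan does not say that they would be. Assume between-person SD 1, record SD 1, m records per person per week, no average change, and SD τ of each person's own change between weeks.

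- Variance assumed by a pooled unpaired comparison: 2(1 + 1)/(nm) = 4/(nm).
- True variance: 2/(nm) + τ²/n = (2 + mτ²)/(nm).
- Ratio of true to assumed: (2 + mτ²)/4. It exceeds 1, so that false positives exceed 5%, only when mτ² > 2. The formula is approximate, since it ignores the small contribution of τ² to the total variance.

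Examples: at m = 14 and τ = 0.25 the ratio is (2 + 0.875)/4 = 0.72; at m = 14 and τ = 0.5 it is (2 + 3.5)/4 = 1.375. Simulation with the pooled rank sum test (4,000 runs per cell) follows the same pattern:

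| τ | n | m = 14 | m = 50 | m = 100 |
|---|---|---|---|---|
| 0.25 | 10 | 3% | 9% | 19% |
| 0.25 | 20 | 2% | 9% | 17% |
| 0.5 | 10 | 10% | 30% | 44% |
| 0.5 | 20 | 9% | 29% | 43% |

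At τ = 0 the rate is about 1%. The signed-rank test on each person's weekly means stays at 4% to 6%. The 14 records are 2 sessions × 7 days at one record per session, following "The participant is instructed to use the application two times every day for about twenty minutes"; 50 and 100 are assumptions.

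**The case against.** **It may be a naming slip.** Both sentences describe paired purposes, so rank sum may simply have been written for signed-rank. If so, the power figures do not apply and only the wording is at fault. This is possible and the documents cannot settle it. But the term occurs twice and nothing in the text corrects it. A slip would also leave the unit and periods for the use measures undefined.

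**The t-test is not wrong.** The plan never calls it unpaired, and a paired test is the natural reading for change in one group. This stands: it is silence, not error.

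**The size is assumed throughout.** This also stands. The loss runs from nothing at correlation 0 to large at high correlation, and the simulated data are normal, although a rank test is presumably meant for measures that are not.

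**A stronger reading is not supported.** A reader might infer that the use-log analysis will produce false positives because many records per person will be treated as independent. The plan nowhere says that records will be pooled. Even if they were, the error could go either way: several of the cells above lie below 5%. Nothing in the documents says how much a person's values vary from week to week.

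**The use-log analysis is secondary.** True, and no efficacy claim rests on it. The weight comes from the first paragraph.

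**Conclusion.** The concern holds as a fault of specification. The plan names an independent-samples test for within-participant comparisons in two places, one of them its primary within-group analysis. With one value per participant per period, the consequence is a conservative test and lost power wherever within-person correlation is positive. For an assumed change of 0.5 SD at correlation 0.5 to 0.7, power is 17 to 35 percentage points lower with 10 participants (28 − 11 and 43 − 8) and 27 to 52 points lower with 20 (54 − 27 and 76 − 24). At correlation 0 nothing material is lost.

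For the use measures, the direction of any error depends on a unit that the plan does not name. Excess false positives are a possibility under some assumptions, not a finding. The between-group mixed models are not touched by this point. The text should be corrected before analysis; medium confidence, because the term may be a slip and all the sizes rest on assumed inputs.

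**What to change.** **First paragraph.** Change the rank sum test to the Wilcoxon signed-rank test for the within-group Barcelona and CAL analyses.

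**Third paragraph.** Replace the sentence on change in the use measures with:

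> Each use measure will be reduced to one summary per participant for each of two pre-defined periods (for example week 1 and week 2), and the periods compared with a paired t-test or, if the paired differences are not normal by the Shapiro-Wilk test, a Wilcoxon signed-rank test.

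A mixed model with a participant random effect, as already planned for Barcelona and CAL, is an acceptable alternative and keeps the course over the two weeks, which two summaries discard. In either case, report how many participants have no data in the later period.

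**Cost.** Two sentences of wording and no new data. There are three downsides:

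- Participants without later data drop out of the paired test for reaction time and recording length.
- With 5 or fewer pairs the exact signed-rank test cannot reach two-sided 5%: its smallest p-value is 2/2⁵ = 2/32 = 0.0625.
- With very few participants a paired test may still miss a modest change. For 0.3 SD at correlation 0.5, signed-rank power is only 13 / 18 / 24% for n = 10 / 15 / 20.

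### The tests of change over time in app use, reaction time and recording length do not say how participants who cut back or stop enter the comparison, and the rank sum test named is unpaired

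*Combined protocol and SAP*

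**What the plan says.** The third paragraph of the Plan for Statistical Analysis covers "descriptive statistics of the use of the application, e.g., amount of use, reaction times, and recording length, for participants in the experimental groups". After the descriptive summary it adds a test, a t-test or the Wilcoxon rank sum test, whose stated purpose is "to evaluate whether they changed over time with the use of the application".

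The Study Protocol sets a recommendation, "The therapist will prescribe use of the application 2 times per day for 20 minutes", over two weeks at home, but also says that "the participant is free to use the application when and for as long as they want". Pausing, cutting back and stopping are therefore all permitted.

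The plan does not state:
- which periods are compared (days, weeks, or first and last sessions);
- whether the comparison is within participant;
- whether a participant with no later use counts as zero, is treated as missing, or is left out.

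No sample size or expected stopping rate is given. The plan says only that numbers are low.

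**The concern.** Reaction time and recording length exist only when the app is used. A participant who stops in the first week can supply early values but no late ones. An independent-samples test then compares everyone early with continuing users late. If slower participants are more likely to stop, the late group is faster by composition alone.

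Amount of use differs, because non-use has a true value of zero. Whether that zero enters the analysis depends on how the data set is built, which the plan leaves open. If low users stop and are left out of the later period, average use appears to rise when overall use has fallen.

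What is at stake is how the app is described: a gain in speed, or sustained engagement, could be reported when the data show only who stayed.

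**Working it through.** The plan gives no figure to reproduce, so the check asks whether the mechanism works and how large it could be. Sample sizes, stopping rates, variances and the link between stopping and speed are all assumptions.

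**Amount of use, by hand.** Assume 70% of participants use the app 40 min/day in both weeks, and 30% use it 20 min/day in week 1 and then stop.
- Week 1: 0.7 × 40 + 0.3 × 20 = 34 min/day.
- Week 2, stoppers left out: 40 min/day; (40 − 34)/34 = +18%.
- Week 2, stoppers at zero: 0.7 × 40 + 0.3 × 0 = 28 min/day; (28 − 34)/34 = −18%.

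**Amount of use, simulated.** Assume 20 users, usual use averaging 30 min/day (SD 10 between people, 5 within), with the lowest users stopping; 4,000 runs.
- 20% stop: 30.0 becomes 33.3 with stoppers left out, or 26.7 with zeros.
- 40% stop: 30.0 becomes 36.1 with stoppers left out, or 21.7 with zeros.
- Paired on continuing users only, the mean change is about 0. Pairing alone removes the false rise but also hides the fall.

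**Reaction time, shift in the estimate.** Assume log-normal times (SD 0.4 between people, 0.15 within, on the log scale), no change in anyone, and 15 to 30 users. The apparent change in the median, all users early against continuing users late, is:
- correlation of 0.7 to 0.9 between slowness and stopping: about 8 to 10% faster with 20% stopping, and 10 to 14% faster with 30%;
- correlation 0.5: about 5 to 9% faster;
- correlation 0: about 0 to 1%.

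Comparing continuing users with themselves brings the shift to roughly zero.

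**Reaction time, false findings.** A second simulation used standardised values with 70% of variance between people, no true change and 2,000 runs per setting. It counted significant results in the faster direction at two-sided 0.05, for which the nominal rate is 2.5%. Stopping is strongly selective (correlation 0.9) in the last three columns.

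| Users | No stopping, unpaired | 20% stop, unpaired | 40% stop, unpaired | 40% stop, paired |
|---|---|---|---|---|
| 10 | 0.2–0.3% | 1.4–1.5% | 3.8–4.0% | 1.7–2.9% |
| 20 | 0.2% | 1.9–2.2% | 15.9–16.3% | 1.8–2.2% |
| 40 | 0.1% | 7.5–9.1% | 45.2–48.4% | 2.2–2.3% |

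Each cell covers the t-test and the Wilcoxon test of that type. The spurious shift at correlation 0.9 is −0.24 to −0.26 SD with 20% stopping and −0.45 to −0.47 SD with 40%. At correlation 0.5 it is −0.13 to −0.14 SD and −0.24 to −0.26 SD. Paired, it is within 0.01 SD of zero throughout.

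The first column shows a second cost of the unpaired test. It ignores the correlation between a person's two values, so it falls far below its nominal error rate when nobody stops.

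**The case against.** A reader might infer that the plan leaves stoppers out. It does not say so; it is silent. If amount of use is totalled per participant per period, a person who stops gets a zero automatically, and the last paragraph of the plan does use each participant's total use as a variable. The reversal from +18% to −18% needs non-users to be deleted from week 2, which the plan does not propose. This objection stands: the gap is in specification, and the plan does not prescribe an exclusion.

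A reader might also take this as a problem separate from pairing. For reaction time it is not, because comparing the same people with themselves removes the artefact. The plan uses the same test name for its within-group pre/post analyses, so a paired test may be what was meant here too. That is possible, but the test as named is unpaired, and for amount of use pairing on logged values alone is not enough.

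Third, false significant findings are uncommon in small samples. Under the log-normal assumptions they were about 1% or less with 20% stopping, and exceeded 2.5% clearly only with about 30 users and 30% strongly selective stopping (3 to 14%). This also stands, and it limits the harm mainly to the estimate.

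Finally, the analysis is secondary and confined to one arm, and the phrase about change with use may mean only change during use. Support and family help may keep stopping low over two weeks. These points lower the severity, but they do not supply the missing rule.

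**Conclusion.** The concern holds as a gap with a conditional consequence. The plan names an unpaired test and does not say how participants who reduce or stop use enter it. Bias arises only if the test is run unpaired (or non-users are dropped from the later period for amount of use) and if stopping is related to speed or level of use. Under those conditions the assumed examples give a late median about 8 to 14% faster and a use trend whose sign depends on an unstated rule. If stopping is unrelated to speed, the reaction-time shift is about nil.

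The documents do not support saying that the plan discards stoppers, that the use trend will reverse, or that a false significant result is likely at the small sample implied by "because of the low number of subjects". No size was worked out for recording length; the same reasoning applies to it, but its direction is unknown.

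A paired analysis also has a limit. If people stop because their own performance is worsening, the result among continuing users can still look favourable.

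Severity is minor. The Barcelona and CAL comparisons are not affected.

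**What to change.** Revise the third paragraph of the Plan for Statistical Analysis to state that:
- change over time is tested within participants, by paired t-test or Wilcoxon signed-rank test, between two periods fixed in advance, for example week 1 and week 2;
- for amount of use, every participant with the app installed is included and a period without use counts as zero, with known log or phone failures treated as missing;
- for reaction time and recording length, the same participants are compared early and late, and the result is described as applying to continuing users;
- the number contributing to each period, and when the others stopped, are reported.

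This costs a few sentences and minor data handling on the app's use data, with no change to treatment or visits. The use trend may look less favourable, and the reaction-time and recording-length results will cover continuing users only.
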